6 STUDY PERIODS, TREATMENT REGIMENS AND POPULATIONS FOR ANALYSES

6.1 Study Periods

Subjects will complete up to 4 periods in the study: Screening, Treatment, Safety Follow Up, Simultaneous Response and Survival Follow-up. For the purpose of the analysis the periods are grouped into Baseline (includes Screening) and Post-Baseline (includes Treatment and Safety Follow Up for Safety analyses and Treatment and all follow up periods for efficacy analyses only).

6.1.1 Baseline Period

Baseline evaluations or events will be defined as evaluations or events that occur before the date and time of the first dose of study.

The following definitions will apply:

- Pre-treatment AEs will be defined as AEs with an onset date and time prior to but not including the day and time of the first dose of study treatment (or with an onset date prior to the day of first dose of study treatment if time is not collected or is missing)
- Baseline evaluations (laboratory tests, pulse oximetry and vital signs) will be defined as evaluations with a date and time on or prior to the day and time of first dose of study treatment (or with an onset date on or prior the day of first dose of study treatment if time is not collected or is missing)

If there are multiple valid assessments, the assessment that is closest to day (and time if collected) of the first dose of study treatment will be used as the baseline in the analyses. If multiple assessments are collected at the same date (and time, if recorded and not missing), the assessment with the latest database entry date (and time, if recorded and not missing) will be considered as baseline. If same database entry date (and time, if recorded and not missing) or database entry date not available, the assessment with the latest modification date will be considered as baseline.

Tumor assessments will be slotted in the baseline period if assessments are before or on start of the treatment date. Baseline tumor assessment is the last assessment in the baseline period.

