In BMS-986183 dose expansion (Part 2) only, subjects who have disease progression on BMS-986183 monotherapy will be able to receive combination treatment (their current BMS-986183 dose + flat dose of nivolumab, provided that this combination dose has been found to be safe from BMS-986183 and nivolumab dose escalation [Part 3]). This combination therapy option is not applicable during BMS-986183 dose escalation (Part 1). Eligible subjects may receive the combination option after careful evaluation and discussion with the BMS Medical Monitor to determine whether the benefit/risk ratio supports administration of further study therapy. Subjects meeting criteria for retreatment will be treated up to approximately 1 year (17 cycles, with 21 days/cycle) with a dose regimen of the combination of BMS-986183 and nivolumab dose escalation (Part 3). Such subjects must meet the eligibility criteria for receiving the combination of BMS and nivolumab as specified in Table 5.1-3.

If subjects in BMS-986183 dose expansion (Part 2) agree to receive the combination therapy, they must consent to a mandatory biopsy at clinically documented disease progression (see Section 3.3.1). In addition, subjects must wait at least 21 days since their last dose of BMS-986183 before receiving the combination therapy option, but they must receive their first dose of combination therapy within 6 weeks of their last study drug administration. These subjects will follow the assessment schedules in Table 5.1-3 and Table 5.5.1-3.

Subjects who agree to receive the combination therapy will be included in the main analysis up to and including disease progression. After disease progression, subjects who agree to receive the combination therapy will also be analyzed in a subanalysis.

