Vital Signs ^e	X	X	X	X		Body temperature, blood pressure, and heart rate (if Day 0 and C1D1 coincide, record vital signs once).
ECGs	Х	X	X	Х		ECGs should be recorded after the subject has been supine for at least 5 minutes.
ECHO or MUGA	X		X			Must include a quantitative assessment of left ventricular ejection fraction and utilize the same modality for any subsequent assessments. ECHO/MUGA may be assessed up to 72 hours prior to the first dose. Also perform as clinically indicated.
Laboratory Tests	X	X	X	X		Day 0 laboratory values should be obtained within 14 days prior to the start of study drug. If the Day 0 laboratory tests are performed within 72 hours prior to dosing on Day 1 then a single exam may count as both the Day 0 and predose evaluation. Repeat the following if > 6 months since last treatment: hepatitis B surface antigen and hepatitis C antibody (if hepatitis C antibody is positive reflex to hepatitis C RNA) or hepatitis C RNA will be done at screening. Note: Testing for HIV-1 and HIV-2 must be performed at sites where mandated by local requirements.

Procedure ^a	Day 0 b,c	C1 and Beyond D1	ΕΟΤ	FU (30, 60, and 100 Days after Last Dose) (30- and 60-day FU: ± 5 days) (100-day FU: ± 10 days)	Survival FU ^d (±2 weeks)	Notes		
						Urine - Day 1 only, unless clinically indicated. See Section 5.3.2.		
Viral Biomarkers(for HBV and HCV)	Х	Х	Х	Х		For HCV infected, HCV RNA on treatment For HBV infected, HBV DNA on treatment		
Coagulation Panel	Х	Х	Х	Х				
Troponin T or I	Х					As clinically indicated		
Thyroid Panel including TSH, free T3, and free T4	Х	X See note				To be done Q6W. See Section 5.3.2.		
Pregnancy Test	Х	Х	Х	Х		For WOCBP only; see Section 5.3.2.		
PK and Immunogenicity Assessments See Section 5.5.								
Biomarker Assessments See Section 5.6.								
Tumor Assessment Tumor Imaging (See Section 5.3.1)	X		Х	X ^f	X ^g	Day 0 must be within approximately 30 days of C1D1. Then at the start of Cycle 3 and then Q6W thereafter (± 1 week). Scans must be de-identified. See Section 5.3.1.		
Concomitant Treatments	Х	Х	Х	X ^h		Medications administered within 4 weeks of dosing and all antiviral medications taken for any length of treatment 100 days after the last dose of study drug.		

Procedure ^a	Day 0 b,c	C1 and Beyond D1	ЕОТ	FU (30, 60, and 100 Days after Last Dose) (30- and 60-day FU: ± 5 days) (100-day FU: ± 10 days)	Survival FU ^d (±2 weeks)	Notes		
Adverse Event Reporting				(100 uuy 1 0. 2 10 uuys)				

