3 TUMOR RESPONSE EVALUATION AND RESPONSE CRITERIA

3.1 Evaluation of Target Lesions

Complete Response (CR): Disappearance of all target lesions. Any pathological lymph nodes (whether target or nontarget) must have reduction in short axis to < 10 mm.

Partial Response (PR): \geq 30% decrease in the sum of diameters of target lesions, taking as reference the baseline sum diameters.

Progressive Disease (PD): \geq a 20% increase in the sum of diameters of target lesions, taking as reference the smallest sum on study (this includes the baseline sum if that is the smallest on study). In addition to the relative increase of 20%, the sum must also demonstrate an absolute increase of ≥ 5 mm. Note: The appearance of 1 or more new lesions is also considered progression.

Stable Disease (SD): Neither sufficient shrinkage from the baseline study to qualify for PR nor sufficient increase to qualify for PD, taking as reference the smallest sum diameters while on study.

Special notes on the assessment of target lesions

- Lymph nodes: Lymph nodes identified as target lesions should always have the actual short axis measurement recorded and should be measured in the same anatomical plane as the baseline examination, even if the nodes regress to below 10 mm on study. This means that when lymph nodes are included as target lesions, the 'sum' of lesions may not be zero even if CR criteria are met since a normal lymph node is defined as having a short axis of < 10 mm.
- Target lesions that become 'too small to measure': All lesions (nodal and nonnodal) recorded at baseline should have their actual measurements recorded at each subsequent evaluation, even when very small (eg, 2 mm). If the radiologist is able to provide an actual measure, that should be recorded, even if it is below 5 mm.

However, when such a lesion becomes difficult to assign an exact measure to then:

- (i) if it is the opinion of the radiologist that the lesion has likely disappeared, the measurement should be recorded as 0 mm.
- (ii) if the lesion is believed to be present and is faintly seen but too small to measure, a default value of 5 mm should be assigned (note: in case of a lymph node believed to be present and faintly seen but too small to measure, a default value of 5 mm should be assigned in this circumstance as well). This default value is derived from the 5-mm CT slice thickness (but should not be changed with varying CT slice thickness).

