7.5 Safety

Safety analyses will be performed primarily on All Treated Subjects and presented by treatment (“as treated”) and overall. In addition, SAE analyses will be produced using All Enrolled Subjects.

Adverse events (AEs) will be coded according to the most current version of MedDRA and be graded using the NCI Common Terminology Criteria for Adverse Events (CTCAE) version 4.03. Drug-related AEs are those events with relationship to study drug “Related” as recorded on the CRF. If the relationship to study drug is missing, the AE will be considered as drug-related. Serious adverse events consist of AEs deemed serious by the Investigator and flagged accordingly in the CRF and clinical database. Adverse events leading to study drug discontinuation are AEs with action taken = “Drug was discontinued”. Adverse events leading to dose delay are AEs with action taken = “Dose was delayed”.

Listing of adverse events will include all enrolled subjects as SAEs and deaths are collected pretreatment. Summaries of adverse events will include events occurring from the date of first study medication and for up to 60 days (inclusive) after the last dose of study drug for Part 1 and 2 and up to 100 days (inclusive) after the last dose of study drug for Part 3 and 4. Listing of serious adverse events will include all enrolled subjects as SAEs and deaths are collected pretreatment. Listing of non-serious adverse events will include all treated subjects.

When reporting adverse events by CTC grade, summary tables will be provided based on the event with worst CTC grade (independent of relationship to study medication). Subjects will only be counted (1) once at the preferred term (PT) level, (2) once at the system organ class (SOC) level, and (3) once in the ‘Total subject’ row at their worst CTC grade, regardless of SOC or PT.

The analysis of laboratory results will be based on All Treated Subjects. Laboratory results will be categorized according to NCI CTCAE (version 4.03) grade. Baseline is defined as the last non-missing measurement prior to or on the first treatment’s dosing date and time. Summaries of laboratory results include baseline and post-baseline results up to 60 days (inclusive) after the last dose of study drug for Part 1 and 2 and up to 100 days (inclusive) after the last dose of study drug for Part 3 and 4 for subjects who are off treatment.

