For retreated subject in Part 3 and 4, the initial off-treatment period is included in all safety analysis as if the retreated subject were still on treatment in that period of time.

For the analyses (during original assigned treatments) of subjects treated with the combination therapy extension option in Part 2, all the safety assessment will be truncated at the first dose date of the combination therapy. All others will follow regular counting rules. For the analysis of subjects treated with the combination therapy extension option during the combination period, all the safety assessments will be counted from the first dose of combination therapy and up to 100 days after last dose (optional analyses).

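### For the Part 2 combination extension, the SAP restarts safety counting at the first combination dose but leaves baseline before monotherapy, and its BOR and PFS definitions close before the combination starts

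*SAP*

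**What the plan says.** **Baseline.** SAP 6.1.1 defines laboratory and vital-sign baseline as "evaluations with a date and time on or prior to the day and time of first dose of study treatment". For scans it says "Tumor assessments will be slotted in the baseline period if assessments are before or on start of the treatment date" and then "Baseline tumor assessment is the last assessment in the baseline period". SAP 7.5 restates the laboratory rule with the same anchor: "Baseline is defined as the last non-missing measurement prior to or on the first" treatment's dosing time.

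**Extension window.** Protocol 3.1.2.1 keeps extension subjects in the main analysis up to and including progression, then adds: "After disease progression, subjects who agree to receive the combination therapy will also be analyzed in a subanalysis". SAP 7.5 truncates their monotherapy safety data at the first combination dose. For the combination period, "all the safety assessments will be counted from the first dose of combination therapy and up to 100 days after last dose"; the SAP marks these analyses as optional.

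**New data collected.** Protocol Table 5.1-3 sets up a Day 0 visit before the extension, with imaging ("Day 0 must be within approximately 30 days of C1D1") and laboratory tests. Protocol 5.3.2 requires the screening laboratory assessments to be repeated for the extension.

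**Endpoints.** SAP 7.5.8 tabulates worst on-treatment laboratory grade against baseline grade. SAP 4.2.1 ends the BOR window at the earlier of first RECIST progression and the last scan before subsequent therapy, and runs PFS from first study drug to first RECIST progression or death. In Protocol Appendix 6 (section 3.1), partial response is judged against the baseline sum, while progression takes as "reference the smallest sum on study (this includes the baseline sum if that is the smallest on study").

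**The concern.** The plan treats the extension as a new period for counting safety data and collects a fresh set of pre-combination values, but no visible rule uses those values as a baseline. SAP 6.2 lists the four study parts and no extension period, so for a Part 2 subject the literal baseline is the one before monotherapy.

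This subanalysis is the planned look at adding nivolumab after progression on BMS-986183. A result meant to describe the combination should not depend on what happened during monotherapy. A laboratory shift table with its window in one period and its reference in another mixes the two. A response or PFS endpoint that ended before the combination began says nothing about the combination. If the rule is left open, whoever programs the tables must either apply the literal text or choose a baseline with open-label data already in view.

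**Working it through.** The plan gives no figure to reproduce here: the extension is not sized and no operating characteristic is quoted for it. The check sets the rules side by side and applies the RECIST thresholds. The laboratory grades and tumour sums below are illustrative assumptions.

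**1. Laboratory shifts.** Inputs: the SAP 7.5 extension window, the SAP 6.1.1 and 7.5 baseline, and the SAP 7.5.8 shift table. Take ALT at Grade 0 before monotherapy, Grade 2 at Day 0, and Grade 2 as the worst value on the combination.
- As written: baseline 0, worst value in the window 2, tabulated as 0 to 2.
- With Day 0 as baseline: 2 to 2, no shift.

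Nothing changed on the combination, yet the written rule records a two-grade shift. Starting the window at the first combination dose does not prevent this, because the Grade 2 value on the combination lies inside the window.

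**2. BOR and PFS under SAP 4.2.1.** For a subject who crossed over on RECIST progression the order is: first monotherapy dose, progression, first combination dose, combination scans. The BOR window has closed and the PFS event has occurred by the second step. Every combination scan falls outside both endpoints, whichever baseline is used.

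**3. What if only the BOR cut-off were lifted?** Protocol 8.3.2 defines BOR without the progression limit, so this variant is worth testing. Let the original baseline sum be 100 mm, the nadir N mm, and the Day 0 sum the smallest that meets progression, 1.2N. For the values of N below the rise is at least 12 mm, so the 5 mm absolute requirement is met.

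- Partial response against the original baseline needs a sum of at most 0.70 × 100 = 70 mm.
- Shrinkage needed from Day 0 = 1 − 70/(1.2N).
- With Day 0 as baseline it is 30% for every N.

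| Nadir (mm) | Day 0 (mm) | Calculation | Shrinkage from Day 0 needed, original baseline |
|---|---|---|---|
| 100 | 120 | 1 − 70/120 | 41.7% |
| 90 | 108 | 1 − 70/108 | 35.2% |
| 83.3 | 100 | 1 − 70/100 | 30.0% |
| 70 | 84 | 1 − 70/84 | 16.7% |
| 60 | 72 | 1 − 70/72 | 2.8% |

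The break-even nadir solves 70/(1.2N) = 0.70, giving N = 83.3. Above it the original baseline makes partial response harder; below it, easier. At N = 100, a 30% fall from 120 to 84 mm is only 16% below the original baseline and is not a partial response.

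**4. Progression on the original nadir.** A sum that stays at 1.2N is still 20% above nadir and still meets progression. Measured from Day 0 it is unchanged, so stable disease. A lesion that was new during monotherapy would also go on counting as new unless the lesion lists are reset.

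**The case against.** The strongest reply is that little depends on this. The extension safety analyses are optional, no text commits to a shift table for that period, and no formal hypothesis is tested. The number crossing over is unknown and could be zero, since the combination dose must first be found safe in Part 3 and the Medical Monitor consulted. All of that stands, and it limits the weight of the point.

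The reply also disposes of several stronger readings that a reader might infer:

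- *Monotherapy toxicity is carried wholesale into the combination results.* It is not. SAP 7.5 counts from the first combination dose, so adverse events with onset before it are excluded. The exposure is confined to results referenced to baseline, chiefly laboratory shifts.
- *A primary endpoint is inflated.* Laboratory grade shift is a primary endpoint type, but the Part 2 monotherapy safety data are truncated at the first combination dose and keep their correct baseline.
- *The baseline rule pushes response towards none.* The table above shows no single direction. What removes combination-period response and PFS is the closing of the SAP 4.2.1 windows at progression, not SAP 6.1.1.
- *The SAP has no efficacy plan for the extension.* The SAP contents list carries an efficacy heading that the public body lacks, so text may have been removed. Its absence is not held against the plan, and the efficacy part of this point rests only on the visible definitions.

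One could add that a sensible programmer would use Day 0 anyway. Perhaps so, but the written rule says otherwise.

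**Conclusion.** The point holds in a limited form. For the Part 2 extension the SAP moves the safety window and leaves the baseline behind. Extension laboratory shift tables, if produced as written, would credit to the combination any grade acquired on monotherapy and still present. Under the visible BOR and PFS definitions, a subject who crossed over on RECIST progression has no combination-period response or PFS to count. If the original baseline were kept and only the BOR cut-off lifted, the bar for partial response would run from 41.7% shrinkage (nadir 100% of baseline) to 16.7% (nadir 70%), against 30%, so the result could not be read as a combination effect in either direction.

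This assumes that the extension tables are produced, that first dose of study treatment means the first monotherapy dose, and that Day 0 progression is at its minimum of 20% above nadir. The number affected is the number who cross over, out of about 50 planned in Part 2. The main Part 2 efficacy analysis, cut at progression, and the main safety analysis, cut at the first combination dose, are not affected.

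**What to change.** Add one paragraph to SAP 6.1.1, with a matching sentence in 7.5, for the Part 2 combination-extension analyses only:

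- Laboratory and tumour baseline is the last assessment on or before the first combination dose (the Day 0 assessments of Protocol Table 5.1-3).
- Target, nontarget and new-lesion lists and the nadir are reset at the Day 0 scan.
- For the subanalysis, BOR, DOR and PFS are assessed from the first combination dose, so that the progression leading to crossover does not close them; DOR is still measured from first response, now on the combination.
- The main Part 2 analysis keeps its original baseline.

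Vital signs need no change because SAP 7.5.9 only lists them. An ECG re-baseline is not essential because the QT objective in SAP 3.2 concerns monotherapy. The cost is the added wording and a second baseline flag in the datasets; the Day 0 data are already collected.

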6.1.2 Post-baseline period

- On-treatment AEs will be defined as AEs with an onset date and time on or after the date and time of the first dose of study treatment (or with an onset date on or after the day of first dose of study treatment if time is not collected or is missing). For subjects who are off study treatment, AEs will be included in summaries if event occurred within a safety window of 60 days after the last dose of study for BMS-986183 monotherapy dose escalation period (Part 1) and BMS-986183 monotherapy dose expansion period (Part 2) and of 100 days after the last dose of study drug for BMS-986183 and nivolumab combination therapy dose escalation (Part 3) and BMS-986183 and nivolumab combination therapy dose expansion (Part 4).
- On-treatment evaluations (laboratory tests, pulse oximetry and vital signs) will be defined as evaluations taken after the day (and time, if collected and not missing) of first dose of study treatment. For subjects who are off study treatment, summaries will include measurements

within a safety window of 60 days after the last dose of study for BMS-986183 monotherapy dose escalation period (Part 1) and BMS-986183 monotherapy dose expansion period (Part 2) and of 100 days after the last dose of study drug for BMS-986183 and nivolumab combination therapy dose escalation (Part 3) and BMS-986183 and nivolumab combination therapy dose expansion (Part 4).

- Tumor assessments will be slotted in the post-baseline period if assessments are after start of the treatment date.

6.2 Treatment Regimens

Study treatments (as treated) are the dose level assignments of BMS-986183 in monotherapy, and BMS-986183 in combination with nivolumab, and are administered in one of four parts:

- BMS-986183 monotherapy dose escalation (Part 1)
- BMS-986183 monotherapy dose expansion (Part 2)
- BMS-986183 and nivolumab combination therapy dose escalation (Part 3)
- BMS-986183 and nivolumab combination therapy dose expansion (Part 4)

6.3 Populations for Analyses

- All Enrolled Subjects: All subjects who sign an ICF.
- All Treated Subjects: All subjects who receive at least 1 dose of study drug.
- PK Subjects: All subjects who receive at least 1 dose of BMS-986183 monotherapy (and nivolumab in the combination therapy) and have available serum and/or plasma concentration data.
- Biomarker Subjects: All treated subjects for whom PD measurements are available at both baseline and at least 1 other time after treatment.
- Immunogenicity (ADA) Population: All treated subjects who had baseline and at least 1 post-treatment immunogenicity assessment
- ECG Evaluable Population: All treated subjects who had a baseline ECG and at least 1 on-study ECG.
- Response Evaluable Population: All treated subjects who had baseline tumor measurement and at least 1 other tumor measurement after treatment, clinical progression, or death prior to the first on-treatment tumor assessment.
- Nivolumab subjects treated beyond progression: All subjects who received at least one dose of nivolumab after the date of initial progression per RECIST v1.1.

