Retreatment may be allowed in BMS-986183 and nivolumab dose escalation (Part 3) and BMS-986183 and nivolumab dose expansion (Part 4) of this study for subjects with disease progression during follow-up. Subjects who complete approximately 1 year (17 cycles, with 21 days/cycle) of study therapy and who enter survival follow-up with ongoing disease control (CR, PR, or SD) for reasons other than drug-related toxicity may be eligible for retreatment, upon subsequent confirmed disease progression within 12 months of the last dose of study drug (on a case-by-case basis) after careful evaluation and discussion with the BMS Medical Monitor to determine whether the benefit/risk ratio supports administration of further study therapy. Subjects meeting criteria for retreatment will be treated up to approximately 1 year (17 cycles, with 21 days/cycle) with the originally assigned dose regimen (eg, same dose and dose schedule administered during the first approximately 1 year [17 cycles, with 21 days/cycle]) or modified dose regimen, unless that dose and schedule were subsequently found to exceed the MTD, in which case the subject will be treated at the next lower or alternate dose and schedule. Subjects entering this phase will follow the schedule as outlined in Table 5.1-3. Samples for PK will be collected less frequently (Table 5.5.1-3).

Response Follow-up Period

Subjects with SD, PR, or CR at study drug discontinuation will continue to have radiologic and clinical tumor assessments at least every 3 to 4 months during the survival follow-up period (Section 3.1) until progression, death, or initiation of new treatment (whichever occurs first).

Radiological tumor assessments for subjects who have ongoing clinical benefit may continue to be collected after subjects complete the survival follow-up period of the study. Subjects who have disease progression following treatment with study drug will not be evaluated for response beyond the EOT visit and will be allowed to receive other tumor-directed therapy as required.

3.1.1 Dose Escalation (BMS-986183 Dose Escalation [Part 1] and BMS-986183 and Nivolumab Dose Escalation [Part 3])

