4.5.7 Treatment Beyond Disease Progression in BMS-986183 and Nivolumab Combination Therapy

Accumulating evidence indicates a minority of subjects treated with immunotherapy may derive clinical benefit despite initial evidence of PD.⁴⁶

Subjects treated with BMS-986183 and nivolumab combination therapy may be permitted to continue combination therapy beyond initial RECIST v1.1-defined PD, as assessed by the investigator, as long as they meet the following criteria:

- Investigator-assessed clinical benefit
- Tolerance of study drug
- Stable performance status

- Treatment beyond progression will not delay an imminent intervention to prevent serious complications of disease progression (eg, central nervous system [CNS] metastases).
- Subject provides written informed consent prior to receiving additional combination treatment. All other elements of the main consent including description of reasonably foreseeable risks or discomforts, or other alternative treatment options will still apply.

A radiographic assessment/scan should be performed within 6 weeks of initial investigatorassessed progression to determine whether there has been a decrease in the tumor size or continued PD. The assessment of clinical benefit should be balanced by clinical judgment as to whether the subject is clinically deteriorating and unlikely to receive any benefit from continued treatment with combination therapy.

If the investigator deems that the subject continues to achieve clinical benefit by continuing treatment, the subject should remain on the study and continue to receive monitoring according to the Table 5.1-2.

Discontinuation due to Further Progression (Confirmed Progression)

For the subjects who continue combination therapy beyond progression, further progression is defined as an additional 10% increase in tumor burden with a minimum 5 mm absolute increase from time of initial PD. This includes an increase in the sum of diameters of all target lesions and/or the diameters of new measurable lesions compared to the time of initial PD. Combination therapy should be discontinued permanently upon documentation of further progression.

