All subjects will complete up to 4 study periods: screening (up to 28 days), treatment (for approximately 1 year or 17 cycles, with 21 days/cycle), safety follow-up (for a total of 60 days after the last dose of study drug for BMS-986183 dose escalation (Part 1) and BMS 986183 dose expansion (Part 2) and for a total of 100 days after the last dose of study drug for BMS 986183 and nivolumab dose escalation (Part 3) and BMS 986183 and nivolumab dose expansion (Part 4)), with simultaneous response and survival follow-up periods. All subjects will continue to be followed up to 6 months from last dose of study drug. Subjects in BMS 986183 and nivolumab dose escalation (Part 3) and BMS 986183 and nivolumab dose expansion (Part 4) may also be eligible for retreatment with their originally assigned dose regimen with disease progression during follow-up. Only subjects in BMS-986183 dose expansion (Part 2) who have disease progression may be eligible for a combination therapy extension option (their current BMS-986183 dose + flat dose of nivolumab, provided that this combination dose has been found to be safe from BMS-986183 and nivolumab dose escalation (Part 3)). Subjects treated with BMS-986183 and nivolumab combination therapy may be permitted to continue combination therapy beyond initial RECIST v1.1-defined PD, as assessed by the investigator, as long as they meet the criteria specified in the protocol (Section 4.5.7). See [Figure 2.1- 2](#) for a schematic of study periods

Figure 2.1- 2: Dosing (Every 3 Weeks) and Study Periods

^a DLT Assessment Period is only for BMS-986183 dose escalation (Part 1) and BMS-986183 and nivolumab dose escalation (Part 3).

^b Response follow-up is simultaneous with survival follow-up. Only subjects with SD, PR, or CR will be followed for response at least every 3 to 4 months until progression, death, or initiation of new treatment (whichever occurs first).

C = Cycle 1 D = Day.

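### The SAP's nivolumab beyond-progression population also admits Part 2 extension starters and retreated Part 3/4 subjects, who did not continue nivolumab through progression

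*SAP*

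**What the plan says.** SAP section 6.3 lists a population for nivolumab treatment beyond progression and defines it as "All subjects who received at least one dose of nivolumab after the date of initial progression per RECIST v1.1". That sets two conditions: a nivolumab dose, and a date later than the first RECIST v1.1 progression. It does not mention study part, earlier nivolumab, continuity of treatment or retreatment.

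The documents allow nivolumab after progression by three routes.

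- **Continuation.** Under protocol section 4.5.7, subjects on the combination "may be permitted to continue combination therapy beyond initial RECIST v1.1-defined PD, as assessed by the investigator", if further conditions are met.
- **Part 2 extension.** Under protocol section 3.1.2.1, "subjects who have disease progression on BMS-986183 monotherapy will be able to receive combination treatment". SAP section 2.1 repeats this: "Only subjects in BMS-986183 dose expansion (Part 2) who have disease progression may be eligible for a combination therapy extension option".
- **Retreatment.** Under protocol section 3.1, Part 3 and 4 subjects who complete about a year of therapy and enter follow-up with disease control "may be eligible for retreatment, upon subsequent confirmed disease progression within 12 months of the last dose of study drug".

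SAP section 2.1 describes the three routes in separate sentences and cites protocol 4.5.7 only for continuation.

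**The concern.** The population's name and the rationale in protocol 4.5.7 both refer to staying on immunotherapy after initial progression. The SAP definition is wider. A Part 2 subject who progresses on BMS-986183 alone and then starts nivolumab is continuing nothing: it is that subject's first nivolumab on study. A retreated subject progressed while off drug, after a period of disease control. Outcomes after progression in these two groups do not describe what happens when the combination is carried through progression.

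The groups also differ at entry. Part 2 enrols previously treated subjects and Part 4 untreated ones, and retreatment is open only to subjects selected for disease control at the end of about 17 cycles. A pooled post-progression summary would therefore have no clear interpretation.

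**Working it through.** The documents give no size or rate for this population, so there is no figure to reproduce. The check is to apply the two SAP 6.3 conditions to each route.

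| Route | Source | Nivolumab on study before first PD? | On nivolumab at first PD? | Meets SAP 6.3? | Continuation under 4.5.7? |
|---|---|---|---|---|---|
| A. Continuation | Protocol 4.5.7 | Yes | Yes | Yes | Yes |
| B. Part 2 extension after RECIST PD | Protocol 3.1.2.1; SAP 2.1 | No | No | Yes, at the first nivolumab dose | No |
| C. Part 3/4 retreatment after RECIST PD | Protocol 3.1 | Yes | No | Yes, at the first retreatment dose | No |

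**Does another rule remove B or C?**

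- SAP 7.5 has a counting rule for retreatment: "For retreated subject in Part 3 and 4, the initial off-treatment period is included in all safety analysis". This governs the safety window, not membership.
- SAP 7.5 also truncates the original-treatment safety data of Part 2 extension subjects at the first combination dose and makes the combination-period analysis optional. It too covers safety only.
- Protocol 3.1.2.1 adds a subanalysis of extension subjects after progression. It does not take them out of the SAP 6.3 population.

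No rule narrows the definition.

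**What would a display by part do?** Protocol 4.5.2 keeps subjects in their original arm, so B would fall under Part 2. A and C both belong to Parts 3 and 4 and would stay mixed.

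**Which endpoints are touched?** Under SAP 4.2.1, the BOR window closes no later than first documented RECIST progression, ORR is built on BOR, and DOR and PFS end at progression or death. A nivolumab dose after first progression cannot change them. Only post-progression summaries of this population are exposed.

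**Scale.** By the planned numbers in SAP 2.1, Parts 2, 3 and 4 can receive nivolumab: 50 + 21 + 50 = 121 subjects, of whom Part 2 is 50/121 = 41%. Parts 3 and 4 together are 71. Let E, C and R be the numbers in the extension, continuing and retreated. The share not continuing is (E + R)/(E + C + R). Uptake is not in the documents. For illustration only, assume 10% to 40% of Part 2 take the extension, 10% to 40% of Parts 3/4 continue, and 0% to 10% of Parts 3/4 are retreated.

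- Lowest: E = 5, C = 28.4, R = 0, giving 5/33.4 = 15%.
- Highest: E = 20, C = 7.1, R = 7.1, giving 27.1/34.2 = 79%.

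A range this wide shows only that the share is unknown.

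**The case against.** The strongest reply is that nothing visible depends on this population. It appears only in the SAP 6.3 list. The efficacy results section is not in the available text, and that cannot be counted as an omission. A reader might infer that benefit in new nivolumab starters will be reported as benefit of continuing beyond progression; the documents do not show this. They also set no objective or hypothesis on treatment beyond progression, and protocol 4.5.7 says its further-progression criteria serve subject management only. All of this stands and limits the consequence.

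A second reply is that results are normally shown by dose, regimen and part, so Part 2 would be separate. SAP Table 7.4.1-1 gives scheduled nivolumab only for Parts 3 and 4, which suggests those parts may have been meant. This stands against the inference that any result must mix all three situations. It does not separate continuation from retreatment within Parts 3/4, and the suggested intent is not written into the definition.

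Third, not every extension subject is caught. Entry to the extension requires disease progression without naming RECIST, so a subject with only clinical progression and no RECIST date falls outside. The extension and retreatment also need case-by-case discussion with the medical monitor, and retreatment has narrow entry conditions. This too stands.

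Finally, limiting the population to Parts 3 and 4 would go too far. Protocol 4.5.7 speaks of subjects on the combination without naming parts (although a footnote to Table 5.1-2 names only Parts 3 and 4), so an extension subject who progresses again on the combination and stays on it could arguably qualify. The fix allows for this.

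**Conclusion.** The definition is too wide for its name. Applied as written, it classes Part 2 extension subjects with RECIST progression on monotherapy, and Part 3/4 subjects retreated after RECIST progression off drug, as treated beyond progression, although neither group continued nivolumab through it. The plan draws this distinction in SAP 2.1 and 7.5 and loses it in 6.3.

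The reach is narrow. A pooled summary would mix three situations; a display by part would still mix two in Parts 3/4. PFS and the SAP-defined BOR, ORR and DOR are unaffected. The 15% to 79% range rests wholly on assumed uptake, so a reader should not conclude that most of the population is misclassified; the number cannot be estimated from the documents. The conclusion rests on a literal reading of SAP 6.3 and on at least one subject entering by the extension or retreatment route.

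**What to change.** Redefine the population in SAP 6.3 along these lines: subjects whose RECIST v1.1 PD occurred while on nivolumab-containing combination therapy and who then continued that therapy under protocol 4.5.7, excluding doses given as retreatment or as the start of the Part 2 extension.

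Flag Part 2 extension subjects and retreated subjects, and report each as a separate group. For extension subjects, count any PD on the combination from the start of the combination period, so that those who continue past it can be identified.

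The cost is one revised definition and derivation flags. SAP 7.5 already requires retreated and extension subjects to be identified for the safety rules. Data collection, sample size and clinical rules do not change. Settling this before analysis avoids a later choice about who counts.
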